#### **1.6.4. Follicular Lymphoma and Other Indolent Lymphomas (iNHL); (FL/iNHL)**

Follicular lymphoma is the most common indolent NHL (iNHL), accounting for about 20 to 30% of all B-cell NHL [19, 55]. Nearly 90% of cases have a translocation [15, 19], resulting in deregulated expression of BCL2. Follicular lymphoma has several grades depending on various histologic features; however, Grade 3B is usually treated like DLBCL [19, 25, 55]. Although they have differing histologies, the other iNHLs such as SLL (discussed below), Waldenström's macroglobulinemia (WM), and marginal zone lymphoma (MZL) often have similar clinical presentations, histories, and treatments as does FL, and are often included in the iNHL category along with FL [56].

Although advanced disease is not curable, effective therapy is available for this disease. Therapy is usually initiated when symptoms are present or certain criteria are met [55]. Rituximab has had a major influence on the treatment of follicular lymphoma and other iNHLs. Typical front-line treatments include rituximab as a single agent, or combined with chemotherapy such as CHOP, bendamustine, or other agents [19, 55, 57]. These agents may also be used in the relapsed setting. High dose chemotherapy with autologous or allogenic stem cell rescue has also been used as a salvage therapy with some success as well [57, 58].

A certain percentage of FLs will transform into DLBCL, which is associated with a poor clinical outcome. The underlying reasons for transformation are unknown, and the risk of transformation is about 2 to 3% per year [26]. These patients are treated like patients with DLBCL.

For patients whose disease has progressed after multiple therapies, several agents have been used, and the PI3 kinase inhibitor, idelalisib, has been approved by the US FDA and other regulatory agencies for use in patients with FL whose disease has progressed after 2 prior therapies [19, 58, 59]. This agent has a response rate of over 50% and a median duration of response of 12.5 months [59]. Further agents are needed for patients with multiple relapsed and/or refractory FL and other iNHLs.

### **1.6.5. Chronic Lymphocytic Leukemia (CLL)/Small Lymphocytic Lymphoma (SLL)**

CLL is the most prevalent leukemia in the western world. SLL is essentially a more nodal form of the disease without peripheral blood involvement [19, 55]. In 2015, there were an estimated 14,620 cases and 4,650 deaths from CLL/SLL.

CLL/SLL is grouped with the indolent lymphomas and is incurable; however, typically it is treatable. Depending on the stage, genetic/other prognostic factors and symptoms at diagnosis, patients may be observed initially and only treated when symptoms such as adenopathy or cytopenias develop [19, 55, 60].

There are a multitude of regimens available for therapy and the choice of 1 regimen or agent over another depends on the patient's prognostic factors, performance status, and symptoms. For more elderly patients with comorbidities, chlorambucil (alone or in combination with obinituzumab or ofatumumab, both anti-CD20 antibodies) can be used. The combinations have shown superior outcomes vs. single-agent chlorambucil [19, 60, 61]. Alternatively, bendamustine with rituximab can also be used. For more fit patients, fludarabine may be used in combination with rituximab and cyclophosphamide (for both upfront and relapsed/refractory patients) [19, 60, 61].

Unfortunately, patients will ultimately relapse or become refractory to most therapies. In some cases, patients may have a histologic transformation of their CLL to DLBCL (Richter's syndrome), and these patients have a poor prognosis [19, 62, 63]. For patients who relapse from previous cytotoxic therapies, such as bendamustine and rituximab, or fludarabine, cyclophosphamide and rituximab, the options are limited especially if the duration of response is fewer than 2 to 3 years [64]. Newer agents are available: Ibrutinib, an inhibitor of Bruton's tyrosine kinase (BTK) was recently approved for the treatment of CLL for patients with relapsed/refractory disease [21, 61, 65]. In addition, idelalisib, an inhibitor of PI3 kinase, was also approved for the treatment of CLL in combination with rituximab for patients with relapsed CLL with comorbidities [49, 66]. Lastly, venetoclax, an inhibitor of BCL2, has shown dramatic activity in relapsed/refractory CLL, although the patients treated in this study had CLL that was relapsed/refractory to fludarabine or alkylator-based therapy [67]. However, patients will relapse from or be refractory to these newer agents, and in the case of relapse from ibrutinib, the prognosis is dismal, with a median survival of approximately 3 months [68]. New therapies are needed for patients who progress or are refractory to the current ones.

In CLL, the detection of minimal residual disease (MRD) is an independent predictor of OS and PFS in patients treated with chemoimmunotherapy [69]. The prognostic value of achieving MRD negativity is unknown with newer pathway inhibitors, and it remains a patient of clinical investigation. MRD assessment has traditionally been done by flow cytometry (typical limit of detection at 1 in 10,000 cells), although other assessments that are perhaps more sensitive are being studied [69-71].

## 2.0 OBJECTIVES AND ENDPOINTS

See [Table 3](#) for definitions of the specialist terms and response criteria used in the sections that follow.

### 2.1. Objectives

#### 2.1.1. Phase 1 Objectives (Escalation)

##### 2.1.1.1. *Primary Objective*

- To determine the maximum tolerated dose/maximum administered dose (MTD/MAD) of cerdulatinib in patients with relapsed/refractory chronic lymphocytic leukemia (CLL), small lymphocytic lymphoma (SLL) or B-cell non-Hodgkin lymphoma (NHL).

##### 2.1.1.2. *Secondary Objectives*

- To make a preliminary assessment of the antitumor activity of cerdulatinib in patients with relapsed/refractory CLL/SLL or B-cell NHL, as assessed by overall response rate (ORR), defined as complete response (CR)+ partial response (PR).
- To assess the safety and tolerability of cerdulatinib.
- To determine the pharmacokinetic (PK) profile of cerdulatinib.
- To evaluate the pharmacodynamics (PD) of cerdulatinib.

#### 2.1.2. Phase 2a Objectives (Exploratory)

##### 2.1.2.1. *Primary Objective*

- To assess the antitumor activity of cerdulatinib in patients with specific subtypes of B-cell or T-cell NHL, or CLL/SLL, as a single agent and in combination with rituximab for B-cell NHL.

##### 2.1.2.2. *Secondary Objectives*

- To assess the duration of antitumor activity of cerdulatinib, amount of time to achieve tumor response, and magnitude of response.
- To further evaluate the PK profile of cerdulatinib in patients with specific subtypes of B-cell or T-cell NHL, alone or in combination with rituximab for B-cell NHL.
- To further evaluate the PD of cerdulatinib in patients with specific subtypes of B-cell or T-cell NHL, alone or in combination with rituximab for B-cell NHL.
- To assess tumor phenotype and genotype in relation to clinical response.
- To further evaluate the safety and tolerability of cerdulatinib in patients with specific subtypes of B-cell or T-cell NHL, or CLL/SLL.

- To evaluate the safety and tolerability of the combination of cerdulatinib with rituximab for B-cell NHL.

### **2.1.2.3. Exploratory Objectives**

- To evaluate the relationship between markers of inflammation with clinical outcome and overall health as determined by the Global Health Assessment.
- To assess Minimal Residual Disease (MRD) status in CLL/SLL patients achieving a complete response/complete response incomplete blood count recovery/partial response (CR/CRi/PR) by flow cytometry. MRD negativity (MRD-) is defined as < 1 tumor cell in 10,000 leucocytes. MRD+ (MRD positivity) is defined as  $\geq 1$  tumor cell in 10,000 leucocytes.

## **2.2. Endpoints**

### **2.2.1. Phase 1 Endpoints**

#### **2.2.1.1. Primary Endpoint**

- The primary safety endpoint will be the incidence of DLT by dose level.

#### **2.2.1.2. Secondary Endpoints**

- ORR, defined as CR+PR.
- Clinical benefit rate, defined as CR + PR + SD, PFS, and DOR.
- Adverse event profile (classified by National Cancer Institute Common Toxicity Criteria for Adverse Events [NCI-CTCAE v4.0]) by dose level.
- Clinically significant changes in vital signs, physical exams by dose level.
- Changes in hematology and chemistry laboratory parameters by dose level.
- PK endpoints: PK profile at each dose level and overall, including  $C_{max}$ , AUC, and  $t_{1/2}$ .
- PD endpoints: Changes in biomarker data for a range of *ex vivo* assays.

**2.2.2. Phase 2a Endpoints****2.2.2.1. *Primary Endpoint***

- The primary efficacy endpoint is ORR, defined as CR+PR.

**2.2.2.2. *Secondary Endpoints***

- Duration of response (DOR), progression-free survival (PFS), time to treatment response (TTR), and lymph node response (LNR).
- Clinical benefit rate, defined as CR + PR + SD.
- Adverse event profile (classified by NCI-CTCAE v5.0) by dose level.
- Clinically significant changes in vital signs, physical exams by dose level.
- Changes in hematology and chemistry laboratory parameters by dose level.
- PD endpoints: Changes in biomarker data for a range of *ex vivo* assays.

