### **3.1.2.2. Rationale for Initial Starting Dose and Individual Dose Reductions**

#### **3.1.2.2.1. Rationale for Starting Dose**

Under Amendment 4 the starting dose of cerdulatinib in the Phase 2a portion of the study was 35 mg BID based on the PK/PD and PK/AE relationships and PK modeling of the Phase 1 study (Section 1.5). Clinical PK/PD evaluations demonstrated that IC50s in the 0.2 to 0.6 μM range suppress BCR and cytokine JAK/STAT signaling pathways (Figure 1). However, under Amendment 5, the starting dose was changed to 30 mg BID (rationale below), with subsequent dose reductions to 25 mg BID, 20 mg BID, and then 15 mg BID permitted (the rationale for individual dose titration strategy is in Section 3.1.2.2.2). Under Amendment 7 starting doses of 30, 25, or 20 mg BID may be explored to further investigate the relationships between cerdulatinib exposure, extent of SYK/JAK pathway inhibition, anti-inflammatory response, clinical response, and safety. The data overall will be used in the final determination of the appropriate dose for registration studies.

IC90 for BCR signaling is approximately 0.8 μM, and for JAK/STAT signaling ranges from 0.75 to 1.25 μM. The pathway inhibition is selective, as no inhibition of JAK2- or PKC-dependent signaling was observed. These data reflect pathway inhibition in peripheral blood, and therefore do not predict the level of inhibition in solid tumor.

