#### 11.1.1. Analysis Populations

The safety analysis population will consist of all patients treated with at least 1 dose of study medication (cerdulatinib). Safety data will be summarized by dose level, based on the original assigned dose of study drug.

The efficacy analysis population for the primary and secondary efficacy endpoints will consist of all patients who have taken at least 1 dose of study medication and have had at least 1 post-baseline tumor assessment. Efficacy will be summarized separately for Phase 1 and 2a, and within Phase 2a, efficacy will be summarized by cohort and dose level.

The PK and PD analysis populations will consist of all patients who have received the requisite treatments and have data at the required time points. Any windows for timing of measurements, etc., will be specified in the SAP.

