#### **11.1.6. Safety Analyses, Phase 1 and 2a**

The primary safety endpoint is the incidence of Grade 3 or higher clinically significant toxicity by dose level, and the secondary safety endpoints are as follows:

- Adverse event profile (classified by NCI-CTCAE v5.0).
- Clinically significant changes in vital signs, physical exams by dose level.
- Changes in hematology and chemistry laboratory parameters by dose level.

The incidence of Grade 3 or higher clinically significant toxicity will be summarized and listed by dose cohort for Phase 1.

Adverse events (AEs) will be graded according to the NCI-CTCAE v4.0 (Phase 1) and NCI\_CTCAE v5.0 (Phase 2a) and coded according to the latest MedDRA version available at the time of database creation. The number and percent of patients with any AE will be presented by System Organ Class (SOC) and preferred term for each cohort will be summarized by dose

cohort for Phase 1 and by Cohort for Phase 2a. An additional summary will include all patients who received the dose used in Phase 2a.

Vital signs, laboratory parameters, and ECG intervals will be summarized and listed by time point for each dose cohort for Phase 1 and by Cohort for Phase 2a. No formal statistical analyses are planned.

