7.9. Safety Analysis

All safety analyses will be performed in the safety analysis population.

Safety will be primarily assessed on the basis of adverse events (AE) rates. Clinical laboratory data, ECG findings, physical examinations, and vital signs will also be used for determining safety. Descriptive statistics will be used to summarize the safety data. The Phase 1 portion will be summarized by the initial assigned dose level and the Phase 2a portion will be presented by cancer type.

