- Rituximab-related TEAEs by SOC, PT (Cohort 2 only)
- Rituximab-related TEAEs by SOC, PT, and maximum severity grade (Cohort 2 only)
- Serious TEAEs by PT
- Serious TEAEs by SOC, PT
- TEAEs leading to cerdulatinib discontinuation by PT
- TEAEs leading to cerdulatinib discontinuation by SOC, PT
- TEAEs leading to cerdulatinib reduction by PT
- TEAEs leading to cerdulatinib reduction by SOC, PT
- Fatal TEAEs by PT
- Fatal TEAEs by SOC, PT.

TEAEs leading to rituximab dose modifications and discontinuations will be listed only.

Summaries (all-grade and grade 3 or above) will be provided for cytopenia category by combining following preferred terms in the AE dataset:

- Neutropenia: neutropenia, neutrophil count decreased, febrile neutropenia
- Thrombocytopenia: thrombocytopenia, platelet count decreased
- Anaemia: anaemia.
- Leukopenia: leukopenia, white blood cell count decreased
- Lymphopenia: lymphopenia, lymphocyte count decreased

For the following categories of TEAEs of special interest, the time to the first onset of the event will be analyzed (e.g. median/mean and min/max).

- All-grade gastrointestinal disorders of special interest
- Grade 3 or higher gastrointestinal disorders of special interest
- All-grade infections of special interest (lower respiratory bacterial infections)
- Grade 3 or higher infections of special interest (lower respiratory bacterial infections)

The relationship between all-grade infections of interest and concomitant compliance use of antimicrobial prophylaxis will be explored. In addition, gastrointestinal disorders and infections of special interest may be analyzed for certain population subgroups as appropriate.

In addition, selected safety summaries will be repeated for the subset of phase 2a subjects with 30 mg BID as starting cerdulatinib dose.

A summary of the number of deaths and the primary cause of death, classified by deaths within 30 days of last dose of study drug and deaths beyond 30 days after the last dose, will be provided.

7.8.1.1. Dose limiting toxicity in Phase 1

The number and percentage of patients experiencing dose limiting toxicities as captured in the eCRF by the investigator during Phase 1 will be summarized by initial dose cohort.

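### Phase 2a safety endpoints are defined by dose level, but no planned summary shows the 35, 25 or 20 mg BID starters separately, and the SAP does not declare the change

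*Protocol*

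**What the plan says.** The protocol gives two answers on how Phase 2a safety is to be tabulated.

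**By dose.** Protocol 2.2.2.2 lists "Adverse event profile (classified by NCI-CTCAE v5.0) by dose level" and "Changes in hematology and chemistry laboratory parameters by dose level" among the Phase 2a secondary endpoints, and words the vital-sign and physical-examination endpoint the same way. Protocol 11.1.1 states: "Safety data will be summarized by dose level, based on the original assigned dose of study drug". Protocol 3.1.2.2.1 explains why starting doses of 30, 25 and 20 mg BID were allowed: to relate exposure, pathway inhibition, response and safety. It adds: "The data overall will be used in the final determination of the appropriate dose for registration studies".

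**By cohort.** Protocol 11.1.6 uses dose groups for the Phase 1 AE tables only; its wording runs "cohort for Phase 1 and by Cohort for Phase 2a. An additional summary will include all patients who received the dose used in Phase 2a". It treats vital signs, laboratory parameters and ECG intervals likewise, and the synopsis repeats this.

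**The SAP.** Section 4.1.2 keeps the dose wording for the Phase 1 safety endpoints; section 4.2.2 omits it for Phase 2a. Section 7.9 says "the Phase 2a portion will be presented by cancer type", and section 7.1 sets the same default. The one dose-specific Phase 2a safety output is in 7.8.1 (Adverse Events): "selected safety summaries will be repeated for the subset of phase 2a subjects with 30 mg BID as starting cerdulatinib dose". Section 8 lists departures from the protocol, including the restricted efficacy analyses, the switch to dominant mass response and the mixed CTCAE versions. The dropped by-dose safety summaries are not among them.

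**The concern.** Phase 2a patients did not all start at one dose. The starting dose was 35 mg BID under Amendment 4, 30 mg BID from Amendment 5, and 30, 25 or 20 mg BID from Amendment 7. A table by cancer type combines whichever of these doses each cohort received. A reader of the combined clinical study report could see the safety profile of FL or PTCL patients, but not the profile at each starting dose, and the protocol says dose information is wanted for selecting a registration dose.

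Dose matters here on the protocol's own account. The reduction from 35 to 30 mg BID followed a safety review of 12 patients, in which 3 accumulated drug beyond the expected time to steady state. Two of those 3 had fatal infections and one had Grade 3 chemical pancreatitis. The protocol says causality cannot be determined, but it lowered the dose to give an extra safety margin.

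**Working it through.** No alpha, power or sample-size figure is at issue. The check compares the texts, with some arithmetic on what the planned tables can show.

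**Step 1: endpoint against planned summary.**

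| Phase 2a safety endpoint (protocol 2.2.2.2) | Protocol 11.1.6 | SAP output |
|---|---|---|
| AE profile, by dose level | by Cohort, plus one summary at the Phase 2a dose | by cancer type; selected repeats for 30 mg BID starters |
| Vital signs and physical examinations, by dose level | vital signs by Cohort | vital signs by cohort; physical examinations listed |
| Hematology and chemistry, by dose level | by Cohort | no dose column stated, so the by-cancer-type default applies |

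Of the four starting doses (35, 30, 25, 20 mg BID), one has a dedicated output and that output is partial. Three have none. The protocol disagrees with itself (2.2.2.2 and 11.1.1 against 11.1.6 and the synopsis), and the SAP takes one side without saying so.

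**Step 2: how different the combined doses are.** Protocol Table 7 gives observed Cmin of 0.38 μM at 20 mg BID and 1.06 μM at 35 mg BID. The ratio is 1.06/0.38 = 2.8.

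**Step 3: the 35 mg BID experience.**
- The protocol's own figure is 3 patients of 12 with continued accumulation. 3/12 = 25%, as stated; exact (Clopper-Pearson) 95% CI 5.5 to 57.2%.
- Fatal infections: 2/12 = 16.7%; exact 95% CI 2.1 to 48.4%.

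The 12 are those in the initial review. The final number of 35 mg BID starters is not given, nor is their cohort.

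**Step 4: what the 30 mg BID repeat recovers.** Where a summary is among those repeated, the 30 mg BID patients can be subtracted from the all-dose table. What remains is the mixture

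(n35·r35 + n25·r25 + n20·r20) / (n35 + n25 + n20),

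where n is the number of patients and r the event rate at each dose. The highest and lowest doses stay together. The documents give neither the split nor the rates, so the following is an illustration on assumed values. The SAP states no all-cohort column; the arithmetic applies to any column with these proportions.

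| Assumed n at 35/30/25/20 mg | Assumed rates (%) | All doses | Remainder after removing 30 mg |
|---|---|---|---|
| 12/188/20/20 | 50/40/30/20 | 91.2/240 = 38% | 16/52 = 31% |
| 12/188/20/20 | 60/50/35/20 | 112.2/240 = 47% | 18.2/52 = 35% |
| 12/108/60/60 | 50/40/30/20 | 79.2/240 = 33% | 36/132 = 27% |
| 12/108/60/60 | 60/50/35/20 | 94.2/240 = 39% | 40.2/132 = 30% |

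The assumed gradient from 35 to 20 mg is 2.5-fold (50/20) or 3-fold (60/20). The tables would show one contrast, 30 mg BID against everything else, of 40 against 27 to 31% or 50 against 30 to 35%. The 35, 25 and 20 mg BID rates cannot be separated.

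**The case against.** The best defence is that the SAP carries out the protocol's most specific text on safety analysis. Section 11.1.6 asks for Phase 2a tables by Cohort plus one summary at the Phase 2a dose; SAP 7.9 plus the 30 mg BID repeat is close to that. This stands: the conflict starts in the protocol and needs resolving there too. It does not explain why the endpoint wording was dropped without mention in section 8.

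The defence can also say that information on dose is not lost. TEAE, laboratory and vital-sign listings are planned, relative dose intensity is indexed to the initial assigned dose, fatal TEAEs and causes of death have their own summaries, and PK and PD analyses go to separate reports. This also stands, and it rules out a stronger reading that a reader might infer: that safety is shown only by cancer type and the dose-toxicity question cannot be answered. A partial contrast and the raw listings will exist. A listing is still not a summary of a defined endpoint.

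A reader might also take the protocol 11.1.6 statement "The primary safety endpoint is the incidence of Grade 3 or higher clinically significant toxicity by dose level" as a Phase 2a commitment, given the section's title. The documents do not support that. The same section summarises that incidence by dose cohort for Phase 1, the synopsis ties the primary safety endpoint to Phase 1, and the Phase 2a primary endpoint is ORR. The point rests on 2.2.2.2 and 11.1.1.

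Finally, the sponsor set the starting dose over time without randomisation, the 25 and 20 mg BID doses were only ones that might be explored, and their numbers are not given. These facts limit what by-dose tables can show. They do not remove the mismatch.

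**Conclusion.** The point holds as a gap between stated endpoints and planned summaries. Three Phase 2a safety endpoints defined by dose level have no matching by-dose analysis, 35, 25 and 20 mg BID starters have no summary of their own, and SAP section 8 is silent. The primary endpoint is unaffected.

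The numerical effect cannot be stated from the documents. It would be tempting to say that the two fatal infections vanish in a table of about 240 patients. That does not follow: the SAP plans columns by cancer type, the cohorts of the first 12 patients are not given, and fatal events are tabulated separately. What can be said is that any 35 mg BID signal is mixed with other doses to an unknown extent, and that causality for those events is undetermined. Nor does any document report better safety at lower doses; the planned tables would simply not show whether it is better. The table in step 4 rests entirely on assumed splits and rates, and serves only to show that removing the 30 mg BID group does not separate the other three.

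**What to change.** 1. In SAP 7.9, add descriptive summaries by initial assigned dose (35, 30, 25, 20 mg BID) for the key TEAE, Grade 3 or higher, serious, fatal, discontinuation and reduction, exposure, vital-sign and laboratory tables. Pool over the single-agent cohorts (1, 3, 4, 5, 6) and show Cohort 2 separately, so that rituximab toxicity is not mixed in. Repeat within FL and PTCL where numbers allow.
2. Restore the dose-level wording in SAP 4.2.2.
3. Reconcile protocol 2.2.2.2 and 11.1.1 with 11.1.6 and the synopsis. If the sponsor decides against by-dose summaries, declare and justify that in SAP section 8.
4. Label the tables as non-randomised and descriptive: starting dose is confounded with enrolment period, cohort and CTCAE version (4.03 or 5.0).

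The cost is SAP wording and repeat runs of existing table programs. Initial assigned dose is already needed for relative dose intensity and for the 30 mg BID subset, so no new data are required. The downside is small, possibly near-empty cells at some doses and the risk of over-reading them. For scale, 8 of 20 (40%) has an exact 95% CI of 19.1 to 63.9%.
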